6.1 Summary of potential risks

Participants allocated to receiving the ketogenic feed could be susceptible to ketoacidosis if the ketones are not metabolised. This could exacerbate pre-existing systemic and cellular acidosis that carries a mortality risk to critically ill patients. There is a possibility that ketogenic diets can also minimise exogenous glucose delivery, predisposing patients to hypoglycaemia, which is harmful.³⁵ Lastly, ketogenic enteral feeds with a high lipid content could increase the risk of vomiting (and therefore pulmonary aspiration), and diarrhoea. However data from previously studies including our recently published trial (ASiCS) does not support concerns of acidosis, hypoglycaemia or vomiting, indicating that the feed is safe.^{34,37-45} It may be that ketogenic feeding reduces glucose variability and hypoglycaemia, decreasing harm to patients, an observation also seen in other ketogenic feeding trials in the critically ill.^{34,46,47} The signal for increased diarrhoea is unclear, as diarrhoea is extremely common in critically ill patients.³⁶

6.2 Summary of potential benefits

The signal for efficacy is consistent across carbohydrate, lipid and amino acid metabolism, biochemical signatures of muscle protein homeostasis and clinical physical function. If this is confirmed in this trial, the novel ketogenic enteral feed will decrease muscle wasting in the sickest of patients and may mitigate the muscle loss seen in early critical illness, providing a new treatment to improve function and well-being in critical care survivors. Further, if the decrease in hypoglycaemia and insulin therapy is confirmed, ketogenic feeding may represent a lower risk of harm to patients than conventional enteral feeding.

7. Trial objectives, endpoints and estimands

7.1 Primary objective

- To assess and draw inference on the efficacy of a 10-day ketogenic enteral feeding compared with standard enteral feeding in increasing the number of sit-to-stand repetitions performed in 30 seconds, 30 days after randomisation in critically ill patients.

7.2 Secondary objectives

- To assess and draw inference on the difference between a 10-day ketogenic enteral feeding regimen compared with standard enteral feeding for the Core Outcome Set

measures of functional recovery (mortality, SF-36, Barthel Index) 30 days after randomisation.

- To provide safety data on the use of a 10-day ketogenic enteral feeding regimen compared with standard enteral feeding during the 10-day intervention period in critically ill patients.

7.3 Mechanistic objectives

- To collect routinely measured daily serum urea and creatinine data during the 10-day intervention period as biochemical markers of catabolism.
- To examine alterations in the causal pathway between arms (differential ketone and amino acid flux, urea cycle flux and tricarboxylic acid cycle intermediate generation) using serum metabolomics from samples on day 1 and 7 post-randomisation.
- To confirm the induction of ketosis by the 10-day ketogenic enteral feeding regimen at seven days post randomisation.

7.4 Primary outcome measure

- The number of sit-to-stand repetitions performed in 30 seconds 30 days after randomisation.⁴⁸

7.5 Secondary outcome measures

- Core Outcome Set measures:⁴⁸
 - All-cause mortality within 30 days of randomisation
 - All-cause mortality within 90 days of randomisation
 - Barthel Index at 30 days after randomisation
 - Short Form 36 quality of life questionnaire at 90 days after randomisation
- PICUPS or PICUPS community questionnaire Index at 30 days after randomisation

7.6 Safety outcome measures

- New (post initiation of intervention) metabolic acidosis (Base Excess of >4 mEq/l) not in keeping with the clinical condition, in the opinion of the treating clinician within 10 days of randomisation.
- Hypoglycaemia episodes not in keeping with the clinical condition (normoglycaemia defined as 4.0-10.0 mmol/l), assessed from routine blood monitoring within 10 days from randomisation.

- Hyperglycaemia episodes not in keeping with the clinical condition (normoglycaemia defined as 4.0-10.0 mmol/l) assessed from routine blood monitoring within 10 days from randomisation.
- Days when an episode of diarrhoea (defined as a Bristol School Score ≥ 5) is recorded on nursing observation charts during the first 10 days from randomisation.
- Days where an episode of vomiting is recorded on nursing observation charts during the first 10 days from randomisation.
- Nausea defined as when an anti-emetic is given for patient-reported nausea assessed daily during the first 10 days from randomisation.

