Ketogenic feeds may help patients regain independence by maintaining muscle mass

Ketogenic feeding involves stimulating hepatic synthesis of ketone bodies. Hepatic metabolism of medium-chain triglycerides (MCTs) can yield ketone bodies such as beta-hydroxybutyrate and acetoacetate and is not affected by hypoxia or inflammation.²³

Ketogenic feeding represents a frame shift in critical care nutritional research. Ketone derived energy would increase muscle protein synthesis and decrease muscle protein breakdown. Ketones are used for energy in high-intensity exercise and starvation, sparing muscle.²⁴⁻²⁷ Ketogenic diets have been used to treat epilepsy and are being investigated for use in traumatic brain injury, neurodegenerative diseases, non-alcoholic fatty liver disease, diabetes and heart failure.²⁸⁻³³

A proof-of-concept trial demonstrated safety, feasibility and a signal for efficacy

We performed a randomised controlled trial to determine the feasibility and safety of delivering a ketogenic enteral feed in critically ill patients as step-change intervention to prevent muscle wasting and loss of physical independence.³⁴ This was necessary for a number of reasons. Ketoacidosis might occur if ketones were not metabolised, exacerbating pre-existing systemic and cellular acidosis that carries a mortality risk to critically ill patients. Ketogenic diets minimise exogenous glucose delivery, which might predispose patients to hypoglycaemia, which is harmful to patients³⁵. Lastly, a ketogenic high lipid feed might increase the risk of vomiting (and therefore pulmonary aspiration), diarrhoea and pancreatitis.³⁶

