8.3 Inclusion criteria

Adults (≥ 18 years) admitted to Critical Care who are:

EITHER:

- Hospitalised with acute respiratory failure (PaO₂/FiO₂ ratio of ≤ 39.9 KPa) *
AND
- Expected to require advanced respiratory support (High-Flow Nasal Oxygen, non-invasive or invasive ventilation for >48 hours)^{\$}
AND
- C-reactive Protein ≥ 75 mg/l indicating systemic inflammation*
AND
- Nasogastric feeding planned for >48 hours^{\$}

OR

- In multi-organ failure (Sequential Organ Failure Assessment Score [SOFA] Score ≥ 2 in two or more domains) *
AND
- Nasogastric feeding planned for >48 hours^{\$}

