8.4 Exclusion criteria

- Pre-existing inability to perform a sit-to-stand test (e.g., significant cognitive impairments that would impact their ability to engage in physical activity testing, significant neurological conditions such as Parkinsons Disease, Parkinsonism, Clinical Frailty score of ≥ 6 , amputations, vascular mobility problems, acute or chronic disability expected to impair or preclude the sit-to-stand test at 30 days, amongst others)^{\$}
- New (i.e., pre-randomisation) inability to perform a sit-to-stand test (e.g., primary neuromyopathy, acute intracerebral pathology, new or existing weight-bearing restrictions or new neurological impairment, amongst others)^{\$}
- Deemed unlikely to survive to 30 days OR presence of a treatment limitation^{\$}
- Contraindications to nasogastric feeding[^]

- Need for specialist elemental feeds[^]
- Patients with known inborn errors of metabolism[^]

* Most recent recording from the first 24 hours of hospital admission

^{\$} as confirmed by the treating clinician

[^] absence of these criteria in the medical notes will be considered to indicate no concern

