18.3 Notification and reporting of AEs and ARs

The AE will be documented in the participants' medical records and the electronic Case Report Form (eCRF). The participant will be followed up by the research team until the AE is resolved.

The following safety events will be required for daily reporting from the point randomisation until day 10 and recorded in the eCRF. These events won't be reported as AEs:

- Acid-Base balance disruption, defined as unexpected acidosis not in keeping with the clinical condition, in the opinion of the treating clinician. The absence of documentation in the medical notes will be considered to indicate no concern.
- Hypoglycaemia episodes (normoglycaemia defined as 4.0-10.0 mmol/l), assessed from routine blood monitoring. Where no routine blood monitoring occurs, normoglycaemia is assumed.
- Hyperglycaemia episodes (normoglycaemia defined as 4.0-10.0 mmol/l) assessed from routine blood monitoring. Where no routine blood monitoring occurs, normoglycaemia is assumed.
- Diarrhoea defined as a Bristol School Score ≥ 5 .
- Vomiting defined as $>10\text{ml}$ of vomitus.
- Nausea defined as when an anti-emetic is given for patient-reported nausea.

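### The 7.6 acidosis outcome counts only new acidosis, so it omits worsening of an acidosis present before the first feed (a risk named in 6.1), and 18.3 defines the event differently

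*Protocol*

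**What the plan says.** **The risk.** The Introduction (section 5) says "Ketoacidosis might occur if ketones were not metabolised, exacerbating pre-existing systemic and cellular acidosis". Section 6.1 repeats the point for participants given the ketogenic feed: "This could exacerbate pre-existing systemic and cellular acidosis that carries a mortality risk to critically ill patients".

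**Who can enter.** Section 8.3 admits acute respiratory failure with inflammation or, by the second route, "In multi-organ failure (Sequential Organ Failure Assessment Score [SOFA] Score ≥ 2 in two or more domains", each with nasogastric feeding planned. Neither route has an acid-base criterion. The only metabolic exclusion in section 8.4 is "Patients with known inborn errors of metabolism".

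**The outcome.** Section 7.6 counts "New (post initiation of intervention) metabolic acidosis" that meets a base-excess threshold and that the treating clinician finds unexplained by the illness, within 10 days of randomisation.

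**The daily report.** Section 18.3 asks sites to record, from randomisation to day 10, acidosis that is unexpected and that the clinician cannot explain by the illness. It does not require the acidosis to be new and gives no base-excess value. It adds: "The absence of documentation in the medical notes will be considered to indicate no concern". These events are recorded in the eCRF but are not reported as adverse events.

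**The concern.** The stated risk includes deepening of an acidosis that is already there, and the entry criteria let such patients in. The outcome meant to detect the risk is nevertheless worded so that an acidosis present when feeding starts is not new, however much it deepens.

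Providing safety data is a secondary objective (7.2). The DMEC reviews safety data, and evidence of harm in the intervention group is a ground for ending the trial (20.3). A low count under 7.6 could be read as reassurance about acidosis in general, when it speaks mainly to acidosis arising after the feed began. Because 7.6 and 18.3 describe the event differently, it is also unclear which definition the final comparison and the DMEC reports will use.

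**Working it through.** The protocol states no acidosis rate and no power for safety outcomes, so there is no figure to reproduce. The check is a comparison of the text.

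| Element | 7.6 outcome | 18.3 daily event |
|---|---|---|
| Must be new | Yes, after the intervention starts | No |
| Base-excess threshold | Yes | No |
| Clinician must find it unexplained by the illness | Yes | Yes, and unexpected |
| Window | Within 10 days of randomisation, after feed start | Randomisation to day 10 |
| Nothing written in the notes | Not addressed | Counts as no concern |

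Three kinds of patient can be followed through these definitions:

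1. **Not acidotic before the feed, becomes acidotic on it.** Countable under 7.6 and recordable under 18.3, if the clinician finds it unexplained.
2. **Acidotic before the feed, recovers, becomes acidotic again within the window.** Can fairly be read as new under 7.6, and is recordable under 18.3.
3. **Acidotic before the feed, and the acidosis deepens without resolving.** Fails the newness condition in 7.6. Recordable under 18.3 only if the clinician judges it unexpected and documents it.

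The third patient is the one sections 5 and 6.1 describe.

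**Other routes for the third patient.** Section 18.3 says its listed events are not reported as adverse events. Section 18.4 limits SAE reports to related and unexpected events, and Appendix 1 exempts worsening organ failure and shock. Section 15.1 restricts collection to data related to outcomes and safety events to be analysed. Neither 7.6 nor 18.3 names a pre-feed acid-base value or a change from one. Worsening may therefore not be recoverable from the database afterwards.

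**Direction and size.** Let q be the share acidotic before the feed, d0 the excess risk of new acidosis on the ketogenic feed in the others, and d1 the excess risk of worsening without resolution among those acidotic at entry. The excess over all participants from these two sources is (1 − q)·d0 + q·d1. The 7.6 wording retains (1 − q)·d0, so the part left out is q·d1. This is positive whenever q and d1 are both positive, and nil if either is zero. The protocol supplies none of q, d0 or d1, so only the direction follows. The loss is in the absolute difference and in the number of events; if the risk ratio were the same in both groups, the counted ratio would not change.

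**Contrast with glucose.** The hypo- and hyperglycaemia outcomes in 7.6 are assessed from routine blood monitoring and carry no newness condition. Among the 7.6 outcomes, only acidosis does.

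**The case against.** A reader might infer that patients acidotic at entry can never register an acidosis event. The documents do not support that. Section 18.3 has no newness condition, so a deepening acidosis can be entered there. An entry acidosis that resolves and recurs fits the 7.6 wording. Deepening while the underlying illness improves is something a clinician could well call unexplained, so such a patient fails the newness condition but need not fail the clinical one.

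A reader might also infer that worsening is the only acidosis risk named. It is not: ketoacidosis comes first in both sections 5 and 6.1, and when new it is covered by 7.6.

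There are further safeguards. Section 9.6 covers refractory acid-base disturbance without requiring it to be new, and unblinding information goes to the DMEC. Section 11.1 promises safety data on acid-base balance in general, and section 12.1 has the DMEC monitor mortality closely. Restricting a safety outcome to clinically unexplained events is also a coherent choice in a population where acidosis from the illness itself is to be expected, and the glucose outcomes in 7.6 carry the same clinical qualifier.

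These points soften the concern without removing it. The 18.3 and 9.6 routes both depend on a clinician, blinded to the feed, attributing the change to something other than the illness, and that is hardest in a patient already acidotic. Under 18.3 an undocumented case counts as none. The numerical size of a worsening criterion can reasonably be left to the SAP. The outcome definition in 7.6, and its conflict with 18.3, are protocol text.

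**Conclusion.** The concern holds in a limited form. As worded, 7.6 leaves unresolved worsening of an acidosis present before the first feed out of the safety outcome, although sections 5 and 6.1 name it and sections 8.3 and 8.4 allow such patients in. Section 18.3 provides a partial route under a different definition, dependent on clinician judgement and documentation. The comparison by arm and the DMEC's view may therefore understate this harm.

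The size cannot be stated. It depends on how many participants are acidotic at entry and on whether the feed worsens their acidosis, and the protocol gives neither. Nothing here implies that the feed does cause acidosis; section 6.1 reports that earlier data do not support that worry. The point is that an outcome kept for this purpose should be able to show the risk it was kept for.

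**What to change.** Reconcile 7.6 and 18.3 into one definition and state that it is the one used for both the final comparison and the DMEC reports:

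- Count new **or** worsening metabolic acidosis.
- Record the last routine acid-base value before the first trial feed.
- Define worsening as a prespecified change from that value, with the amount for the sponsor to set.
- Report by arm for all participants, and separately by acidosis at entry.
- Keep the clinician's attribution as a separate field, so that events can be shown with and without it.

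The cost is one baseline eCRF field and a wording change, using routine measurements. Treatment, eligibility and sample size are unaffected. The downside is that more acidosis from the underlying illness will be counted in both arms; the separate attribution field lets readers see how much.

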11.1 Study intervention risks

Published data on our ASiCS trial that specifically set out to assess safety does not support worries of acidosis, hypoglycaemia, or vomiting.³⁴ The signal for increased diarrhoea is unclear, as diarrhoea is extremely common in critically ill patients. For ASiCS-II, pre-defined safety data will be collected on acid-base balance, glucose control, and gastrointestinal intolerance (specifically on vomiting and diarrhoea). All such side effects would occur during the acute inpatient stay and therefore detected directly by the study team. Furthermore the Data Monitoring and Ethics Committee (DMEC) will monitor safety data throughout the trial and will routinely meet to assess safety analyses.

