20.3 Data monitoring and Ethics committee (DMEC)

The DMEC is independent of the trial coordinating team and comprises of a minimum of two clinicians with experience in undertaking clinical studies and a statistician. The DMEC functions primarily to periodically review overall safety data to determine patterns and trends of events, or to identify safety issues, which would not be apparent on an individual case basis. The committee will also review relevant new external evidence and monitor the overall conduct of the study. The committee will agree conduct and remit, which will include the early termination process. The study will be terminated early if there is evidence of harm in the intervention group or if recruitment is futile. Generally, the CI identifies any relevant external evidence and passes this to the DMEC Chair for review by the DMEC. The DMEC will provide recommendations about stopping, modifying or continuing the study to the TSC. The DMEC may also make recommendations regarding selection, recruitment, or retention of participants, their management, protocol adherence and retention of participants, and

procedures for data management and quality control. The TSC will be responsible for promptly reviewing the DMEC recommendations, to decide whether to continue or terminate the study, and to determine whether amendments to the protocol or changes in study conduct are required.

21. Finance and funding

ASiCS-II is funded by the National Institute of Health Research (**NIHR158620**). The proposal was peer reviewed by internal and external experts during the funding process. Since securing the award, the protocol has since been further reviewed during the study design process.

Nestle Health Sciences will be providing the feed preparation for the participants randomised to the intervention arm.

22. Indemnity

NHS indemnity scheme will apply. It provides cover for the design, management, and conduct of the study.

23. Dissemination of research findings

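### The base-excess threshold for the metabolic acidosis safety outcome in section 7.6 points the wrong way, and section 18.3 defines the same event without any threshold

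*Protocol*

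**What the plan says.** Section 7.6 of the protocol lists the outcome as "New (post initiation of intervention) metabolic acidosis (Base Excess of >4 mEq/l". It adds two further conditions: the event must be "not in keeping with the clinical condition, in the opinion of the treating clinician within 10 days of randomisation". No other base-excess threshold appears in the protocol. The figure is nowhere given a negative sign or called a base deficit.

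Section 18.3 lists the same kind of event among those recorded daily in the eCRF up to day 10, in different terms: "Acid-Base balance disruption, defined as unexpected acidosis not in keeping with the clinical condition, in the opinion of the treating clinician". It gives no numeric threshold and does not require the event to be new since the feed began. It also sets a default for missing information: "The absence of documentation in the medical notes will be considered to indicate no concern".

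The purpose of the outcome is clear from elsewhere. The risk summary in section 6.1 opens with this: "Participants allocated to receiving the ketogenic feed could be susceptible to ketoacidosis if the ketones are not metabolised". Section 11.1 promises that "pre-defined safety data will be collected on acid-base balance, glucose control, and gastrointestinal intolerance", and says the DMEC will monitor safety data throughout. Section 20.3 states: "The study will be terminated early if there is evidence of harm in the intervention group or if recruitment is futile".

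**The concern.** A positive base excess means a surplus of base, which is the direction of alkalosis. Metabolic acidosis is a deficit of base, so its base excess is negative. The number in section 7.6 therefore contradicts the label it is meant to make precise.

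The outcome is meant to pick up the first hazard that the protocol names for the ketogenic feed. Base excess is the only objective element in its definition; the rest is clinical judgement. A definition that true acidosis cannot satisfy could make the feed look free of this harm whatever happened to the patients.

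Section 18.3 does not settle the matter, because it describes the event differently. A reader cannot tell whether an event needs a base-excess value at all, or whether it must have started after the feed began.

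**Working it through.** The plan has no figure to reproduce here and no sample-size or error-rate formula applies. The check is one of direction and consistency.

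**Step 1. Test the printed inequality.** The table takes four illustrative base-excess (BE) values in mEq/l and asks whether each meets the number. They serve only to show direction and are not trial data. The second column allows for a minus sign lost when the PDF was read.

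| BE (mEq/l) | As printed: BE > +4 | If a minus sign was lost: BE > -4 | Read as a base deficit > 4, i.e. BE < -4 |
|---|---|---|---|
| +6 (base surplus) | meets | meets | fails |
| 0 | fails | meets | fails |
| -6 (base deficit) | fails | fails | meets |
| -15 (base deficit) | fails | fails | meets |

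Neither literal reading selects acidosis. A lost minus sign does not explain the text, because the inequality would still run the wrong way. Label and number agree only if the figure is read as a deficit, and the text calls it an excess.

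**Step 2. Apply the whole entry.** Section 7.6 requires the event to be new, to be metabolic acidosis, to have the stated base excess, and to be out of keeping with the clinical condition in the clinician's opinion. Metabolic acidosis and a base excess above +4 are close to mutually exclusive. Applied as a conjunction, the rule gives almost no events.

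**Step 3. Set the two definitions side by side.**

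| Element | Section 7.6 | Section 18.3 |
|---|---|---|
| Event | metabolic acidosis | unexpected acidosis, under acid-base disruption |
| Numeric threshold | base excess above 4 mEq/l | none |
| New since start of feed | required | not stated |
| Clinician's opinion | required | required |
| Missing documentation | not addressed | taken as no concern |

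The same patient can therefore be an event under section 18.3 and a non-event under section 7.6. A patient at -6 whose clinician finds the acidosis unexpected is one such case.

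**Step 4. Ask what else would show acidosis.** Section 18.3 says its listed events are not reported as AEs. Section 18.4 limits SAE reports to events that are both related and unexpected. Under sections 9.12 and 16, beta-hydroxybutyrate and lactate are measured in samples from days 1 and 7, and section 16.6 has results shared once the last patient's sample has been analysed. The protocol describes no second acidosis outcome.

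**The case against.** The strongest reply is that this is a slip any intensive care clinician would correct on sight. The label says acidosis, and the number is only a gloss on it. Section 18.3, which governs daily recording, has no number, so a clinician following it would record true acidosis whatever is printed in section 7.6. Bedside safety does not rest on the threshold either: section 9.6 provides for stopping the intervention for refractory, unexplained acid-base abnormalities that concern the consultant, without a base-excess cut-off. Section 20.3 ties early termination to evidence of harm in general.

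Much of this stands. It rules out two stronger readings that a reader might infer.

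- **That the outcome would count alkalosis.** This is true of the number taken alone. The entry also requires metabolic acidosis and the clinician's judgement, so an alkalotic patient would not qualify. The literal result is a near-empty outcome.
- **That the DMEC and the final safety table will certainly receive a false all-clear.** Nothing in the protocol says that events are derived by applying the threshold to recorded values. The eCRF and the statistical analysis plan are not at hand, so the derivation is unknown.

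It would also be wrong to call this the trial's only numeric safety threshold. Glucose and stool limits appear in section 7.6, and section 18.3 adds one for vomitus.

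The reply does not remove the error. Relying on each site and the analyst to correct the text silently is not a definition, and section 18.3 supplies a competing definition where section 7.6 needed a correction.

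**Conclusion.** The point holds as a wrong figure in an outcome definition, together with a conflict between sections 7.6 and 18.3. The error in direction is complete: no patient with a negative base excess can meet the printed number. Only the convention that base excess is negative in metabolic acidosis is needed to see this.

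The practical effect is conditional. If the eCRF or the analysis applies the printed number, acidosis would be under-counted, possibly almost to zero. If recording follows section 18.3 alone, clinicians could still capture true acidosis, and what remains is an outcome with two incompatible definitions. The documents do not show which route will be used or how many sites would read the text literally, so no rate of misclassification can be given. They also do not establish that the magnitude of 4 is what was intended.

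The point should be put right before safety data are reported, because it affects the first hazard named for the feed and is easily corrected. No sample size, power or alpha figure depends on it.

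**What to change.** The sponsor should confirm the intended cut-off. Section 7.6 should then state it in the acidosis direction, either as a negative base excess or equivalently as a base deficit. No cut-off is proposed here.

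Sections 7.6 and 18.3 and the eCRF should then carry one definition. It should settle whether a base-excess value is required, whether the event must be new since the feed began, and how missing documentation is treated. Recording the base-excess value beside the clinician's judgement would let the event be checked from data; that is a sensible addition and not part of the correction.

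The cost is a line or two of text in each section and an eCRF check. The change concerns an outcome definition only and leaves every treatment and stopping rule as it is.
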